10.1.4 Demographic history

Participant's date of birth, ethnicity, sex, smoking information will be collected at Visit 1.

10.1.5 Nasal swab

Nasal swab will be collected at four time points (shown in Figure 1).

One swab will be collected from each nostril. Nasal swab will be used for viral detection and identification, including COV.

10.1.6 Blood tests

Venous blood samples will be collected at four time points (shown in Figure 1) for viral serology and immune profiling.

10.1.7 Patient daily symptom data

Following randomisation, the process will be explained to participants concerning their documentation of /response to daily SMS regarding any respiratory symptoms. These symptoms and/or condition related to the symptoms will be recorded as adverse events. Unclear or missing entries will be clarified with the participant and any correction annotated by site staff as appropriate. Annotations made by site staff will be clearly identified and initialled and dated.

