6.3 Known and potential risks

Published clinical trials have reported OM85 to be well tolerated in children and adults. Reports of discontinuation of drug with an adverse event have been reported in three studies; two children from two separate studies discontinued drug due to rash or diarrhoea, and a study in adults with chronic obstructive pulmonary disease or chronic bronchitis reported 5 participants

in the active group (n=142) and 9 participants in the placebo group (n=131) discontinuing investigational product. In most clinical trials the number of participants experiencing adverse events were no different between the active (OM85) and placebo groups¹². In adults, the most common reported adverse events were gastrointestinal, including nausea and diarrhoea. Six studies reported no adverse events. In elderly patients (>65 years), the most common adverse events were disease of the genitourinary (19/147, 13%), “symptoms, signs and ill-defined conditions” (11/147, 7%) and disease of the circulatory system (7/147, 5%).

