8.2.2 Secondary efficacy endpoints

Secondary endpoints include:

- The time to ARI necessitating workforce removal
- The proportion of HCW contracting an ARI necessitating workforce removal at end of treatment and at the end of the follow-up period, overall and by department
- The total number of days with respiratory symptoms (upper or lower)
- The proportion of HCW with COV infection documented by PCR, seroconversion and/or COV ARI necessitating workforce removal.
- The time to LRI necessitating workforce removal
- The proportion of HCW contracting an LRI necessitating workforce removal at end of treatment and at the end of the follow-up period, overall and by department
- The proportion of HCW with COV infection documented by PCR, seroconversion and/or COV LRI necessitating workforce removal.

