10.1.9 Adverse events

[figure not shown]
AEs will be collected from the time the medicinal product is administered. Further information regarding the collection and reporting of AEs can be found in Section 12.

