11.6 Permitted medications during study

During the study, participants will be allowed to take medications routinely used in the management of fever, cough or wheezing attacks, including inhaled and oral steroids. All medications will be recorded in the source documentation and CRF.

12. Assessment of safety

The site investigator is responsible for the assessment and documentation of any event that meets the criteria of an AE (see Section 12.1) or an SAE (see Section 12.2).

AEs and SAEs will be collected from the time of first dose of investigational product until the participant has completed the study at their final visit, even if the participant ceases the investigational product prematurely.

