13.3.3 Safety endpoints

All participants will be included in all safety analyses. All AEs reported during the study will be included in the analysis. The goal of the statistical evaluation of all AE data will be evaluated using a standardised tabulation of frequency and incidence rates of all observed AEs. The frequencies and incidence rates will be calculated on a per patient basis and not on an even basis.

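### Respiratory symptoms count both as an efficacy outcome and as adverse events, so any overall AE rate is mixed with efficacy, in a direction that depends on an unresolved AE start rule

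*Combined protocol and SAP*

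**What the plan says.** Participants in both groups answer a daily SMS about respiratory symptoms after randomisation. Section 10.1.7 adds: "These symptoms and/or condition related to the symptoms will be recorded as adverse events".

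The same information feeds efficacy. Section 8.2.2 lists "The total number of days with respiratory symptoms (upper or lower") as a secondary endpoint, next to ARI and LRI endpoints; ARI with workforce removal is also the primary endpoint (8.2.1).

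For safety, Section 13.3.3 states "All AEs reported during the study will be included in the analysis" and plans a "standardised tabulation of frequency and incidence rates of all observed AEs". On counting it says "The frequencies and incidence rates will be calculated on a per patient basis and not on an even basis", where I read the word before the last as event. It gives no rows or classes, no observation period and no separate presentation of endpoint events. Section 8.3 has safety data go to the DSMB by group. The named safety endpoints in 8.2.4 are narrower: treatment-related AEs and routine laboratory tests.

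On when AEs begin, Section 10.1.9 says "AEs will be collected from the time the medicinal product is administered", and the opening of Section 12 says "AEs and SAEs will be collected from the time of first dose of investigational product". Group 1 receives no drug until Month 3 (8.1).

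**The concern.** An event that the drug is meant to prevent is a poor component of a measure of what the drug harms. When respiratory symptoms sit inside the overall AE rate, a difference between arms in that rate mixes three things: the effect on colds, any true side effects, and any difference in how long or how closely the two arms were observed.

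The side effects to be expected are of another kind. Section 6.3 reports: "In adults, the most common reported adverse events were gastrointestinal, including nausea and diarrhoea". These have no daily prompt, whereas respiratory symptoms are solicited every day. An excess of gastrointestinal events could therefore be a small part of an overall rate made up largely of colds. At stake is whether the DSMB and the final report can read the overall AE and SAE figures as evidence on safety.

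**Working it through.** The plan states no figure on this point, so there is none to reproduce. The check sets the start rules side by side and then works through both readings on assumed rates.

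**Step 1. When do wait-list AEs start to count?**

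| Provision | What it implies | Wait-list AEs in months 0–3? |
|---|---|---|
| 10.1.7 | SMS symptoms become AEs, after randomisation, in either arm | Yes |
| 10.2 and Appendix 1, Group 1 | AE assessment at Visit 2, when drug is first dispensed, with diary review marked there in Appendix 1; AE assessment at the unscheduled ARI visit, with no limit to time after dosing | Yes, by implication |
| 12.3 (SAEs only) | Reporting runs from informed consent | Yes |
| 10.1.9 and opening of 12 | Collection runs from first dose | No |
| 12.1 | An AE presupposes that a product has been given | No |

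The provisions cannot all be followed.

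**Step 2. Inputs.** The documents give no incidence of respiratory symptoms or gastrointestinal (GI) events by arm for this population. Symptom risks of 20%, 40% and 60% in control over 3 months, and GI risks of 3% in control and 8% on OM85, are assumptions. The only anchor is Section 13.2, which assumes 20% in Group 1 and, with both countries, a 25% reduction (20% to 15%). That is for infection or ARI, so it is only a stand-in for symptoms. The two kinds of event are taken as independent:

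any-AE risk = 1 − (1 − symptom risk) × (1 − GI risk)

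**Step 3. Reading A: wait-list symptoms count from randomisation.**

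| Symptoms, control vs OM85 | Any-AE, control | Any-AE, OM85 |
|---|---|---|
| 20% vs 15% | 1 − 0.80 × 0.97 = 22.4% | 1 − 0.85 × 0.92 = 21.8% |
| 40% vs 32% | 1 − 0.60 × 0.97 = 41.8% | 1 − 0.68 × 0.92 = 37.4% |
| 60% vs 48% | 1 − 0.40 × 0.97 = 61.2% | 1 − 0.52 × 0.92 = 52.2% |

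In each row OM85 has the lower overall rate although its GI events are 8/3 = 2.7 times as frequent. The two any-AE rates are equal when (1 − symptom risk on OM85) = (1 − control symptom risk) × 0.97/0.92. That needs a symptom risk on OM85 of 15.7%, 36.7% or 57.8%, which is a relative reduction of 21.7%, 8.2% or 3.6% at control risks of 20%, 40% and 60%. The commoner the symptoms, the smaller the benefit that cancels the excess.

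A second set of assumed side-effect risks, 5% vs 10%, gives the same picture:

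- 20% symptoms with a 25% reduction: 24.0% vs 23.5%
- 40% with a 10% reduction: 43.0% vs 42.4%
- 60% with a 25% reduction: 62.0% vs 50.5%

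**Step 4. No efficacy at all.** With 5% vs 10% side effects and 20% symptoms in both arms, any-AE is 1 − 0.95 × 0.80 = 24.0% vs 1 − 0.90 × 0.80 = 28.0%. By the pooled two-proportion normal approximation (two-sided 0.05), the power to see the excess is 30% at 500 per arm and 53% at 1000 per arm. Tabulated alone, 5% vs 10% gives 85% and 99%. The plan prescribes no AE test, so these figures only gauge how visible the excess would be.

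**Step 5. Reading B: AEs count from first dose.** In months 0–3 the wait-list arm contributes 0% by rule. The OM85 rates of Step 3 then stand at 21.8%, 37.4% and 52.2% against 0%. Nothing is offset: ordinary colds on OM85 have no control counterpart and inflate apparent harm. From the visit times in Section 10.2, AE windows would also run over months 0–6 in Group 2 and 3–9 in Group 1, so the arms would be compared over different infection periods.

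**The case against.** The strongest case against has four parts.

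- **Start of collection.** Sections 10.1.9, 12 and 12.1 agree that AEs need a dose, and on that rule a benefit on colds cannot offset anything. This stands as one side of a conflict. It does not settle the matter, because 10.1.7 and the Group 1 visit schedule point the other way and 13.3.3 includes all participants in all safety analyses.
- **No pooled rate is named.** Each AE gets its own title (12.1). In rows by AE term, GI events would appear as 3% vs 8%, untouched by colds. This stands, and per-patient counting also limits the weight of repeated daily symptoms. But 13.3.3 sets no row structure, and an overall per-patient rate is a natural summary of what it describes.
- **The named endpoint is treatment-related AEs.** A cold judged unrelated does not enter it. This limits the problem but does not remove it. No placebo is described, so site investigators attribute events knowing who is on drug, and an untreated participant cannot have a treatment-related event. In months 0–3 that endpoint therefore has no control comparison. The all-AE comparison avoids attribution, and it is the one affected.
- **Removing respiratory events could hide a respiratory harm of an immunomodulator.** This stands, and is why the fix shows the rates both ways.

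It is also fair that every rate above is assumed, and that Section 6.3 reports no difference in AEs from placebo in most trials.

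**Conclusion.** The double use is documented and nothing else in the protocol undoes it. Any overall AE rate is therefore confounded with efficacy. The direction depends on the start rule: possible masking of side effects if wait-list symptoms count from randomisation, inflated harm if AEs count only from first dose.

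A reader might infer more, namely that a benefit on colds will hide an excess of side effects and make OM85 look safer than it is. The documents do not support that. It needs wait-list symptoms to count before dosing, which three provisions contradict; it needs safety to be judged on one pooled rate, which the plan does not name; and it needs the treatment-related endpoint to be set aside.

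The sizes (41.8% vs 37.4% on one reading, 0% vs 37.4% on the other) follow from assumed risks and independence. They show what the rule can do, not what to expect. Severity is minor to moderate.

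**What to change.** 1. **Reconcile the start rule.** Align Sections 10.1.7, 10.1.9, 10.2, 12, 12.1 and 12.3 and Appendix 1, so that respiratory symptoms, ARI/LRI and AEs generally are ascertained over the same period from randomisation in both arms. Adjust the definition in 12.1 so that an untreated wait-list participant can have a recorded AE.
2. **State the comparison period in 13.3.3.** Use randomisation to Month 3, before the wait-list group starts drug, for the between-group AE comparison, and show later periods separately. Scheduled follow-up is 9 months in Group 1 and 6 in Group 2 (10.2), so whole-study rates from randomisation would not cover equal time.
3. **Separate the tabulation in 13.3.3.** Put efficacy-outcome respiratory events (SMS symptoms, ARI, LRI) in their own table. Show other AEs by term, and give overall AE and SAE rates both with and without the respiratory events, so that a respiratory harm stays visible to the DSMB.

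The cost is protocol wording and one extra table. Daily SMS data and a Month 3 AE assessment are already planned for the wait-list group, so no new visit is needed.

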10.1.8 Telephone calls

Telephone calls may be conducted during the study to ensure patient compliance with investigational product and completion of daily symptom data. If required, telephone calls will be conducted to assess adverse event data and review of concomitant medications and therapies will be undertaken. These may be conducted via SMS or email if participant prefers.

10.1.9 Adverse events

[figure not shown]
AEs will be collected from the time the medicinal product is administered. Further information regarding the collection and reporting of AEs can be found in Section 12.

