10.2 Scheduled visits

This study consists of 5 visits (Group 1 - WLC) or 4 visits (Group 2 – initial treatment) over 6 or 9 months respectively (see Figure 1) Study procedures to be performed at each visit are detailed in the Schedule of Assessments and Procedures in Appendix 1.

Visits should be conducted within the specified visit windows where possible.

Figure 1: Study timeline and procedures. Nasal swab collection (blue arrow), blood collection (red arrow).

Group 1 (WLC)

Visit 1 – Screening and randomisation

The following assessments and procedures will be performed and recorded at this visit:

- Obtain written informed consent
- Evaluate inclusion and exclusion criteria
- Obtain demographic history
- Obtain medical history
- Vital signs
- Explain daily respiratory symptom data collection and assist with collection for Day 0

Once all screening procedures have been completed and eligibility confirmed, the participant will be registered with the Sponsor. Further information on the registration process is provided in the Study Reference Manual.

Visit 2: Treatment initiation 3 months post randomisation (±5 days)

- Update demographic & medical history
- Vital signs

- Nasal swab
- Collection of blood samples
- Dispense study medication and explain administration
- Adverse event assessment

Visit 3: Treatment cessation 6 months post randomisation (± 5 days)

- Vital signs
- Nasal swab
- Collection of blood samples
- Clarify any missing data (daily respiratory symptoms) with participant, if not previously addressed by email/SMS
- Adverse event assessment
- Collect used investigational product packaging and unused investigational product

Visit 4: Follow up cessation 9 months post randomisation (± 5 days)

- Vital signs
- Nasal swab
- Collection of blood samples
- Clarify any missing data (daily respiratory symptoms) with participant, if not previously addressed by email/SMS
- Adverse event assessment

Unscheduled Visit: at time of ARI necessitating workforce removal

- Vital signs
- Nasal swab
- Collection of blood samples
- Clarify any missing data (daily respiratory symptoms) with participant, if not previously addressed by email/SMS
- Adverse event assessment

Group 2 (Initial Treatment)

Visit 1 – Screening, randomisation, and treatment initiation

The following assessments and procedures will be performed and recorded at this visit:

- Obtain written informed consent
- Evaluate inclusion and exclusion criteria
- Obtain demographic history

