12.1 Adverse events

In accordance with the TGA GCP guidelines (CPMP/ICH/135/95), an AE is any untoward medical occurrence in a participant administered a medicinal product and which does not necessarily have a causal relationship with this treatment. An AE can therefore be any unfavourable and unintended sign (including an abnormal laboratory finding), symptom, or disease temporally associated with the use of the investigational product, whether or not considered related to the investigational product.

All AE should be well documented in the participant's source notes and CRF. Start and stop dates, outcome and whether the participant required treatment will be recorded. The site investigator will determine the title of the AE, severity, relationship to investigational product and seriousness.

An AE does not include:

- Pre-existing disease or condition that was present prior to the first administration of the investigational product, and that does not have a clinically significant increase in severity and/or frequency during the study
- Medical or surgical procedures. The disease or condition that led to the procedure should be recorded as the AE, not the procedure itself.

AEs will be followed up until they have returned to baseline status or stabilised. Follow-up of AEs should continue until the overall clinical outcome has been ascertained or the final visit completed.

If an AE later escalates to meet the criteria for a SAE (see Section 12.2), then it must be reported to the Sponsor as an SAE. See Section 12.3 for Investigator's responsibilities for reporting SAEs.

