12.3 Investigator’s responsibility for reporting serious adverse events

All SAEs will be reported within 24 hours of the site staff becoming aware of the event. The SAE (Initial) Form will be completed and faxed to the Sponsor on [contact] using all information known at the time. A minimum of the SAE title, onset date and date the last investigational product was delivered should be provided, and if possible, the form should be reviewed and signed by the site investigator prior to faxing.

Further guidance on SAE reporting, including instructions for completion of the SAE form can be found in Study Reference Manual.

If site staff becomes aware of new information regarding an SAE, a SAE (Follow Up) form should be completed and forwarded to the Sponsor within five days. New information may include recurrent episodes, complications, or progression of the initial SAE, acquisition of relevant hospital records, reports and/or laboratory results. The follow-up information should describe whether the event has resolved or continues, if and how it was treated, and whether the patient continued or withdrew from study participation.

SAEs, regardless of suspected causality, occurring after the patient had provided informed consent and until 30 days after the patient has stopped study participation/ withdrawn, must be reported. Any SAEs experienced after this 30 day period should only be reported if the Investigator suspects a causal relationship to the study drug. SAEs that are ongoing at the end of the study should be followed up until a final assessment is possible, and until all queries from the Sponsor have been resolved.

In accordance with local requirements, the site investigator must also notify their local EC of any SAEs.

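### The AE and SAE collection windows contradict each other, and the first-dose rule, followed literally, leaves the wait-list group's general AEs in Months 0–3 outside collection

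*Combined protocol and SAP*

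**What the plan says.** **Start at first dose.** Section 10.1.9: "AEs will be collected from the time the medicinal product is administered". The opening of Section 12: "AEs and SAEs will be collected from the time of first dose of investigational product until the participant has completed the study", with the final visit as the end. Section 11.1 puts first dose at Day 0 in Group 2 and Month 3 in Group 1.

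**Start at consent.** Section 12.3 requires reporting of "SAEs, regardless of suspected causality, occurring after the patient had provided informed consent and until 30 days after" the patient stops participation or withdraws.

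**Definition.** Section 12.1 says "an AE is any untoward medical occurrence in a participant administered a medicinal product". It also excludes conditions already present before the first administration, unless they worsen to a clinically significant degree.

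**Passages that reach wait-list participants before dosing.**
- Section 10.1.7, on the daily SMS symptom data that begin at randomisation: "These symptoms and/or condition related to the symptoms will be recorded as adverse events".
- Section 10.1.8: "If required, telephone calls will be conducted to assess adverse event data".
- Section 10.2 and Appendix 1 list an AE assessment at Group 1 Visit 2 (Day 90), the visit at which drug is first dispensed, and at any unscheduled ARI visit.
- Section 10.3 asks participants who leave between visits to complete the next visit's procedures if they agree.
- Section 9.3.1 requires an AE that causes withdrawal to be entered in the CRF.

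**Analysis.** Section 13.3.3 includes all participants and all AEs reported during the study, tabulated per patient, with no period stated. Section 8.3 sends safety data to the DSMB by group. The AE endpoint in Section 8.2.4 is treatment-related AEs.

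**The concern.** In most trials consent and first dose fall close together, so a first-dose rule costs little. Here they are about three months apart in one randomised arm and coincide in the other. A collection rule tied to dosing is therefore a rule tied to allocation.

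The trial has no placebo. Months 0–3 are the only time when treated and never-treated participants are observed side by side. If general AEs are collected in one arm only, a by-group table for that period shows Group 2's background events with nothing opposite them. This includes the gastrointestinal events that Section 6.3 calls the most common in adults. Investigators judging relatedness open-label would have no untreated rate to read against. A DSMB receiving data by masked group could also tell the wait-list group by its lack of such events. If sites resolve the conflict differently, recording will vary between sites as well as between arms.

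**Working it through.** The plan states no figure on this point. The check is a comparison of the passages plus arithmetic on visit days.

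**Inputs.** First dose: Day 90 (Group 1), Day 0 (Group 2) (Section 11.1, Appendix 1). Last scheduled visit: Day 270 (Group 1); 6 months, taken as Day 180 (Section 10.2), or Day 120 (Appendix 1) for Group 2. Group size: 500 per group per country, 1000 per group in all (Synopsis).

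**Step 1: trace a wait-list event in Month 2.**
- *SAE:* outside Section 12 (before first dose), inside Section 12.3 (after consent). This is a direct contradiction.
- *Respiratory symptom:* outside Sections 10.1.9 and 12, inside Section 10.1.7.
- *Non-serious, non-respiratory event:* outside Sections 10.1.9 and 12. If it persists to Day 90, the exclusion in 12.1 can make it a pre-existing condition, and a site could enter it under the medical history update also listed at Group 1 Visit 2. The AE assessment at that visit could capture it, but no look-back period is stated.

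The same three events in Group 2 are collected under every passage.

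**Step 2: trace an SAE after the last visit.** Section 12 has closed. Section 12.3 runs 30 days beyond the end of participation. The end points conflict in both arms.

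**Step 3: collection time for general AEs, Days 0–90, literal first-dose rule.**
- Group 1: 90 − 90 = 0 days per participant. Group 2: 90 − 0 = 90 days.
- With 500 per group: 0 v 500 × 90 = 45,000 person-days. With 1000 per group: 0 v 1000 × 90 = 90,000 person-days, before dropout.

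**Step 4: whole-study windows.**
- From first dose: Group 1, 270 − 90 = 180 days; Group 2, 180 (Section 10.2) or 120 (Appendix 1).
- From randomisation: Group 1, 270 days; Group 2, 180 or 120. Ratios 270/180 = 1.5 and 270/120 = 2.25.

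Moving the start to Day 0 and then comparing whole-study per-patient figures would therefore replace one imbalance with another.

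**Step 5: the month-1 interim.** Section 13.2.2 lets the DSMB consider switching wait-list participants to OM85 at once. If a switch occurred at about one month, untreated wait-list time with 1000 per group would be about 1000 × 1/12 = 83 person-years, against 1000 × 3/12 = 250 for Group 2 over three months. A fixed Day 0–90 per-patient table would then compare unequal follow-up.

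**The case against.** The strongest reply is that the visit schedule, not the start rule, governs practice. The Day 90 AE assessment is ticked in both groups, and in Group 1 it can essentially only look back at untreated time. The SMS, the unscheduled visit and the as-needed calls are the same in both arms, and Section 13.3.3 takes every AE reported. This has force: no visit is missing, and a site following the schedule would record these events. It does not remove the conflict. Section 13.3.3 cannot restore events that a site, following Sections 10.1.9 and 12, never recorded.

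A reader might infer three stronger things that the documents do not support:
- *That a wait-list participant who leaves before Month 3 can never contribute a general AE.* Section 10.3 brings Visit 2's AE assessment forward for those who agree, and Section 9.3.1 requires an AE that causes withdrawal to be recorded. Such events may be missed; they are not ruled out.
- *That the treatment-related AE endpoint is biased by the missing events.* An event before first dose cannot be treatment-related, so that count does not change.
- *That a planned safety comparison is invalid.* Section 13.3.3 specifies tabulation only, with no between-group test.

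It is also fair to say that the person-days above measure observation time, not an effect on any result. The documents give no background AE rate from which an effect could be estimated.

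**Conclusion.** The point stands as a contradiction with an arm-dependent consequence. SAE collection has two start points and two end points. Followed as written, the first-dose rule gives 0 v 90 days of collection of non-serious, non-respiratory AEs per participant over Days 0–90. Whether that happens depends on which passage a site follows, so the loss may lie anywhere from none to complete and may differ between sites.

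What is affected is the all-AE tabulation, the by-group DSMB review and the only concurrent untreated background rate. Treatment-related AE counts and the efficacy analyses are not. The sizes assume full enrolment, no dropout and wait-list dosing at Day 90. The sponsor should correct this early, because pre-dose events not recorded at the time are hard to recover.

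**What to change.** - **Sections 10.1.9, 12 and 12.3:** reconcile to one AE/SAE start at Visit 1 (consent and randomisation) and one stated end point, the same for both arms.
- **Section 12.1:** keep the guideline definition. Add that events in wait-list participants between randomisation and first dose are recorded in the same way and are not treated as pre-existing conditions.
- **Section 10.2, Group 1 Visit 2:** state that the AE assessment covers the time since randomisation. Any general AE prompt added between visits should be identical in both arms.
- **Section 10.2 and Appendix 1:** align on Group 2 Visit 1, where the text lists an AE assessment and the table does not.
- **Section 13.3.3:** tabulate AEs by randomised group over the concurrent period before wait-list dosing. If wait-list participants are switched early after the month-1 interim, use person-time or truncate both arms at the same time. Tabulate events after first dose separately. Do not compare whole-study per-patient rates between groups.

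The cost is wording and more wait-list AE entries; no visit is added. Recall of up to three months at Day 90, and the possibility that open-label reporting differs between arms, should be noted beside the table. The conflicting follow-up lengths in Section 10.2 and Appendix 1 also need reconciling, but as a separate point.
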